Eligible patients are randomly allocated in a 1:1 ratio to the ‘higher PEEP’ or ‘lower PEEP’ strategy. The allocation sequence is computer–generated by an independent investigator using permuted blocks of random size of four, six, and eight patients, and stratified per center. Randomization is performed by local investigators patient–by–patient employing a dedicated, password protected, SSL–encrypted website.

At each site, at least two investigators are involved with the study. One local investigator randomizes the patients immediately before surgery, and is

responsible for the trial intervention and data collection. A second local investigator remains blinded to the assigned treatment, and is responsible for postoperative data collection.

Outcomes

The primary study outcome is a collapsed composite of PPC developing within the first five postoperative days. This endpoint follows the European Perioperative Clinical Outcome (EPCO) definition and has been used before in several clinical trials.²⁻⁴ A patient that develops one or more PPCs is considered as meeting the primary outcome. The components of the composite outcome of PPC have been defined and described elsewhere,¹ and include: 1) aspiration pneumonitis; 2) moderate respiratory failure; 3) severe respiratory failure; 4) acute respiratory distress syndrome (ARDS); 5) pulmonary infection; 6) atelectasis; 7) cardiopulmonary edema; 8) pleural effusion; 9) pneumothorax on the non-surgical lung; 10) pulmonary infiltrates; 11) prolonged air leakage; 12) purulent pleuritic; 13) pulmonary embolism; and 14) lung hemorrhage. The selected PPC can sensibly be merged as they share common pathophysiological mechanisms and have plausibility to be affected in the same direction by the intervention tested in this study.

Secondary outcomes include: 1) extended PPC, including bronchospasm or mild respiratory failure; 2) severe PPC, as defined in a recent published clinical trial⁵ (composite of severe respiratory failure, pneumothorax, ARDS, pulmonary infection, prolonged air leakage, purulent pleuritis, new requirement of non-invasive or invasive ventilation due to respiratory failure and/or atelectasis); 3) a composite outcome of intraoperative complications, including use of continuous positive airway pressure for the non-ventilated lung, use of inhaled nitric

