oxide/prostacycline, use of selective fiberoptic insufflation, hypotension unresponsive to fluids and/or vasoactive drugs, new arrhythmias unresponsive to intervention, need for high dosage of vasoactive drugs, need for massive transfusion, life-threatening surgical complication (including major bleeding, tension pneumothorax and intracranial injury), hypoxemia and hypercapnia rescue maneuvers; 4) postoperative extrapulmonary complications, including systemic inflammatory response syndrome, sepsis, severe sepsis, septic shock, extrapulmonary infection, coma, acute myocardial infarction, acute renal failure, disseminated intravascular coagulation, stroke, hepatic failure, and gastrointestinal failure; 5) need for unexpected intensive care unit admission or readmission; 6) any postoperative respiratory intervention used for respiratory failure (new requirement of non-invasive ventilation or mechanical ventilation); 7) number of hospital-free days at day 28; 8) in-hospital mortality; 9) 90-day mortality; 10) arterial blood gas analysis during surgery (PaO₂, PaCO₂, pH_a). All definitions are available in **Table 1**.

Cleaning and closing of the database

The database will be locked as soon as all data are entered and all discrepant or missing data are resolved, after all efforts are employed to fix missing data, complete the database, and we consider that the remaining issues cannot be fixed. At this step, the data will be reviewed before database locking. After locking, the data will be exported for statistical analysis. At this stage, permission for access to the database will be removed for all investigators, and the database is archived.

Missing data

No or minimal losses to follow-up for the primary outcome is anticipated. Complete-case analysis will be carried out for all outcomes. However, if more than 5% of missing data is found for the primary outcome, a sensitivity analysis using multiple imputations and estimating-equation methods will be carried out. Multiple imputation will consider imputation models based on prognostic baseline and post-baseline variables under a missing at random assumption.

Sample size

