An adaptive trial design is used, which accumulates data and uses external information to modify aspects of the design without undermining the validity and integrity of the trial. The group sequential methods design offers the possibility for early stopping the study if the experimental treatment shows a statistically significant therapeutic advantage at an interim assessment, but also allows early stopping for futility if the interim analysis reveals that, with high probability, the trial will be negative.

PROTHOR is designed to enroll a total of 2378 patients (1189 in each arm). This number allows the detection of a reduction in the incidence of the primary outcome from 23% in the 'lower PEEP' group to 17.25% in the 'higher PEEP' group (relative risk reduction of 25%), considering a type I error of 5%, a power of 90%, similar allocation ratio between the arms (1:1) and a dropout rate of 5%. The required sample size is calculated based on an estimated effect size derived from individual patient data from previous trials,^{3,4,6-9} and the LAS VEGAS study.¹⁰

An alpha-spending function was used to generate efficacy boundaries and a beta-spending function to generate futility boundaries (gamma family spending function, type I error 0.05, type II error 0.1). By using a gamma of -4 for the alpha

and gamma of -2 for the beta spending function a moderate hurdle for early stopping for efficacy and a reasonable chance to stop early due to futility is considered. A non-binding futility boundary was constructed in such a way that it can be overruled if desired without inflating the type 1 error. This flexibility is important, since the data monitoring committee might well prefer to keep the trial going to gather additional information, despite crossing the futility boundary (**Figure 1** and **Table 2**).

Interim analyses

Five interim assessments for evaluation of efficacy, harm, and/or futility were planned, with the aim of possibly stopping the study early. The planned number of assessments describes the number of time points, including the closing date of the study, at which the investigator plans to analyze the thus far collected data. The spacing of assessments will be equal. Therefore, interim analyses were performed after 20% (476 patients), 40% (952 patients), 60% (1426 patients), and 80% (1902 patients) of the planned inclusions, and the final analysis will be performed after 2378 patients (100%) are included (**Table 2**).

Statistical analyses

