Per-protocol analysis

The per-protocol population will consist of patients truly ventilated according to the protocol. Thus, patients will be excluded from this population if receiving PEEP < 10 cm H₂O in the ‘higher PEEP’ group or PEEP > 5 cm H₂O and FiO₂ < 1.0 in the ‘lower PEEP’ group, unless rescue for hypoxemia or hypercapnia required adjustments of PEEP and FiO₂ as defined by the protocol.

Subgroup analysis

Treatment effects on incidence of PPC will be analyzed according to the following predefined subgroups: 1) type of surgery (non-thoracoscopic versus thoracoscopic); 2) positioning (lateral decubitus versus supine position); 3) baseline SpO₂ < 96% versus SpO₂ ≥ 96%; 4) chronic obstructive pulmonary disease (COPD) versus non-COPD; 5) body mass index < 30 kg/m² versus ≥ 30 kg/m²; and 6) duration of one-lung ventilation < 120 versus ≥ 120 minutes. Analyses of heterogeneity of effects across subgroups will be performed with the

use of treatment-by-subgroup term added to the primary model and will be presented in a forest plot.

Other exploratory analyses

Given that the primary outcome of the present study is a collapsed composite, the choice of the statistical method is an important part of designing since various methods provide different power, depending on the situation. In addition to the standard analysis described above, the following analyses will be performed:

- Count analysis: the number of positive component events (i.e., 'count') across the composite will be assessed. The groups will be compared on the count using a Wilcoxon rank sum test, and the odds ratio with the 95% confidence interval will be assessed with a cumulative logistic regression model;
- Individual component analysis: the effect of the intervention in each component will be analyzed estimating the risk ratio and confidence intervals with Wald's likelihood ratio approximation test using a Bonferroni correction for multiple comparisons. The 99.6% Bonferroni-corrected confidence intervals will be reported ($1 - 0.05/14 = 0.996$);
- Common effect test: A multivariate (i.e., multiple outcomes per subject) generalized estimating equations (GEE) model will be used to estimate a common effect odds ratio across the components;

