Prolonged air leakage	Air leak requiring at least 7 days of postoperative chest tube drainage.
Purulent pleuritic	Receiving antibiotics for a suspected infection, as far as not explained by the preoperative patient condition alone.
Pulmonary embolism	As documented by pulmonary arteriogram or autopsy, or supported by ventilation/perfusion radioisotope scans, or documented by echocardiography and receiving specific therapy.
Lung hemorrhage	Bleeding through the chest tubes requiring reoperation, or three or more red blood cell packs.
Bronchospasm	Newly detected expiratory wheezing treated with bronchodilators.
Mild respiratory failure	PaO ₂ < 60mmHg (or < 7.9 kPa) or SpO ₂ < 90% for 10 minutes in room air, but responding to oxygen ≤ 2 L/min.
Systemic inflammatory response syndrome	Presence of two or more of the following: 
 • Body temperature < 36 °C or > 38 °C; • Heart rate > 90 beats per minute; • Respiratory rate > 20 breaths per minute or, on blood gas, a PaCO₂ < 32 mmHg (4.3 kPa); • White blood cell count < 4000 cells/mm³ or > 12,000 cells/mm³, or > 10% band forms.
Sepsis	Systemic inflammatory response syndrome in response to a confirmed infectious process; infection can be suspected or proven (by culture, stain, or polymerase

	chain reaction), or a clinical syndrome pathognomonic for infection
Severe sepsis	Sepsis with organ dysfunction, hypoperfusion, or hypotension), septic shock (sepsis with refractory arterial hypotension or hypoperfusion abnormalities in spite of adequate fluid resuscitation); signs of systemic hypoperfusion may be either end-organ dysfunction or serum lactate greater than 4 mmol/dL, other signs include oliguria and altered mental status.
Septic shock	Sepsis plus hypotension after aggressive fluid resuscitation, typically upwards of 6 L or 40 mL/kg of crystalloid.
Extrapulmonary infection	Wound infection + any other infection.
Coma	Glasgow Coma Score < 8 in the absence of therapeutic coma or sedation.

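### Table 1 defines the primary component purulent pleuritis without mentioning the pleura, so as printed any new antibiotic-treated infection would count as a primary event

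*SAP*

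**What the plan says.** The Outcomes section of the SAP lists 14 components of the primary composite, with purulent pleuritic (sic) as number 12. The scoring rule is "A patient that develops one or more PPCs is considered as meeting the primary outcome". The same component enters the secondary outcome severe PPC, whose list includes "pulmonary infection, prolonged air leakage, purulent pleuritis".

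On where the definitions are to be found, the section says two things. The components "have been defined and described elsewhere", meaning the published protocol. It then closes with "All definitions are available in" Table 1.

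In Table 1 the full criterion for the row purulent pleuritic is "Receiving antibiotics for a suspected infection, as far as not explained by the preoperative patient condition alone". Further down the same table, extrapulmonary infection, a component of a different secondary outcome, is defined as "Wound infection + any other infection".

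The table of modifications from the original plan lists no change to the definition of this component.

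**The concern.** The criterion names no pleura, pus, imaging, drainage or culture. Its only elements are antibiotics, a suspected infection, and an exclusion for the preoperative condition. Since one component suffices, the width of this row sets the width of the primary outcome on the infection side.

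If the printed wording was used, infections outside the chest enter both the primary outcome and severe PPC. Such events do not fit the SAP's own reason for merging the components, which is a shared mechanism and an effect of PEEP in a common direction. Events that PEEP does not influence raise the rate in both arms and shrink the absolute difference that the primary model estimates. If the printed wording was not used, the finalized SAP misstates a component of its primary outcome. Either way the row needs attention before the final analysis.

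**Working it through.** **1. Side-by-side reading of the SAP**

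| Table 1 row | What the criterion requires | Outcome it feeds |
|---|---|---|
| Pulmonary infection | New or progressive infiltrate plus at least two of four items, one of which is antibiotic treatment | Primary, severe PPC |
| Purulent pleuritic | Antibiotics for a suspected infection not explained by the preoperative condition alone | Primary, severe PPC |
| Extrapulmonary infection | Wound infection or any other infection | Extrapulmonary complications |

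Take a patient given antibiotics on day 3 for a new wound infection, with clear lungs and pleura. By the words of Table 1 this patient meets the second and third rows, and so is a primary event, a severe PPC and an extrapulmonary complication. A patient with a suspected chest infection who fails the stricter first row can also enter through the second. The neighbouring rows (prolonged air leakage, pulmonary embolism, lung hemorrhage) are intact and match their labels, so a shifted table row is not the evident cause.

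**2. Reproducing the design**

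Inputs: 23% v 17.25% (Sample size section); N = 2259 before dropout, or 1129.5 per arm; information 0.2 to 1.0 in equal steps; efficacy |Z| 3.252, 2.986, 2.692, 2.374, 2.025; futility |Z| below 0.031, 0.152, 0.631, 1.344, 2.025 (Table 2).

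Drift = (p1 − p2) / √{[p1(1−p1) + p2(1−p2)] / 1129.5} = 0.0575 / √{(0.1771 + 0.1427) / 1129.5} = 3.417.

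Numerical integration over the five looks, with the futility region treated as two-sided, gives efficacy crossing probabilities of 0.042, 0.170, 0.282, 0.263 and 0.143, total 0.900. Table 2 has 0.042, 0.170, 0.281, 0.263 and 0.143. The design reproduces.

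**3. Illustration of dilution**

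The SAP gives no rate, so q is an assumption throughout. In the main case, q is the share of each arm that meets the literal wording independently of a true PPC and unaffected by PEEP. Then p′ = p + q(1 − p), and the difference becomes 5.75 × (1 − q) points. Patients positive on this component only number 1129.5 × q × (0.77 + 0.8275).

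| q | Lower v higher PEEP | Difference (points) | Power | Positive on this component only |
|---|---|---|---|---|
| 0 | 23.00% v 17.25% | 5.75 | 0.900 | 0 |
| 1% | 23.77% v 18.08% | 5.69 | 0.886 | 18 |
| 2% | 24.54% v 18.91% | 5.64 | 0.871 | 36 |
| 5% | 26.85% v 21.39% | 5.46 | 0.824 | 90 |

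In this case power stays at or above 0.85 up to q = 3.4% and at or above 0.80 up to q = 6.5%.

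Alternative assumptions, for q = 1%, 2% and 5%:
- Equal share of patients positive only on this component in both arms (p′ = p + q): difference unchanged at 5.75 points; power 0.890, 0.880, 0.851.
- Such events already contained in both planned rates: no loss.
- Such events already contained in the 23%, with the 25% relative reduction acting only on the rest: higher-PEEP rate = q + 0.75(0.23 − q) = 17.50%, 17.75%, 18.50%; difference 5.50, 5.25, 4.50 points; power 0.872, 0.839, 0.709.

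**4. Would the planned analyses show it?**

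Under Other exploratory analyses, "the effect of the intervention in each component will be analyzed estimating the risk ratio", and the outcomes table has a row per component. These would show how often the component occurred and its own effect. The analyses listed for eTable 11 are the count analysis, the common effect test, the average relative effect test and the test of heterogeneity across components. None reruns the primary model without this component, so none shows how the primary absolute difference depends on it.

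**The case against.** The strongest reply is that a definitions table pairs a name with a criterion, and the name does part of the work. Other rows lean on their labels too: the extrapulmonary infection row, read without its label, would include pneumonia. On that reading the row means purulent pleuritis, operationalised by antibiotics given for it. The SAP also points to a published definition, and neither that nor the case report form is at hand. The missing entry in the modifications table fits a pleural definition that was merely abbreviated here. Overlap with extrapulmonary infection proves little by itself, since nothing makes the two outcomes mutually exclusive. On size, q is assumed, and the worst figure of 0.709 needs literal-only events to make up 0.05/0.23 = 22% of planned control-arm events with no effect of PEEP on any of them. The average relative effect test also keeps one frequent, unaffected component from dominating as it can in the collapsed composite.

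Most of this stands as a limit on the claim. It is not established that the primary outcome was contaminated, and the power figures are illustrations. It does not rescue the row. A label is not a criterion, and this document offers Table 1 as the place where all definitions are found. Applied as written, the row scores the wrong patients. The component-level analyses are useful but answer a different question from the primary model.

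**Conclusion.** The point holds as an internal inconsistency: the label and the criterion of a primary component do not match, and severe PPC inherits the mismatch. Which of the two was collected cannot be decided from the SAP. If the label governed, the harm is confined to a wrong row in a finalized plan. If the printed wording governed, the expected effect is dilution rather than bias between arms, given blinded postoperative data collection. For q of 1% to 5% in the main case, that is a loss of 0.06 to 0.29 percentage points of difference and a fall in power from 0.900 to between 0.886 and 0.824. Across the alternative assumptions the result ranges from no loss to a power of 0.709. The row should be fixed; the possible effect is not negligible and resolving it is cheap.

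**What to change.** Before unblinding for the final analysis, compare the Table 1 row with the case report form and the published definition.

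- **If the definition collected was pleural:** correct the row to say so, and state that infections counted only as extrapulmonary do not qualify.
- **If the printed wording was used:** keep the primary outcome as collected. The SAP reports that "interim analyses were performed after 20% (476 patients") and at later looks, so redefining the outcome now would detach the final analysis from those looks. Pre-specify one sensitivity analysis with the same primary model that does not count this component. Patients positive only on it are scored as having no event and stay in the denominator. Add it to eTable 11. The daily wound-infection and therapeutic-antibiotic items in eTable 7 can help describe these patients, although that table records no other site of infection.

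In either case, use one name for the component; the SAP has both pleuritic and pleuritis.

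The cost is one table row, one check of the case report form and at most one extra model fit. No new data are needed and the primary outcome as collected does not change.
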